4.3 Exclusion Criteria

1. Liver-directed therapy (chemoembolization, radioembolization, bland embolization, ablative therapy) within 4 weeks of DEB-TACE.
2. Previous liver transplantation.

3. Serum bilirubin \geq 6 mg/dl
4. AST > 10 times upper normal limit
5. ALT > 10 times upper normal limit

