3.1 Single DEB-TACE procedure algorithm

Patients who meet the eligibility criteria in Section 4.0 and present with HCC confined to one liver segment supplied entirely by one segmental branch of the hepatic artery the right or the left hepatic artery will be offered a single DEB-TACE treatment intended to target the entire tumor vasculature. The following algorithm will be adhered to for patients with disease confined to one liver lobe or segment:

One to sixty days prior to treatment, patients will undergo imaging of the abdomen with contrast-enhanced CT or MRI. Within one to six days prior to DEB-TACE, laboratory tests including CBC, BUN, creatinine, coagulation panel, liver function tests, and serum alpha-fetoprotein level (AFP) will be performed. A history and physical examination will be performed within six days prior to and the day of DEB-TACE (Table 1).

For the purposes of DEB-TACE procedure, hepatic angiogram will be performed in the standard fashion via a common femoral artery approach. Coaxial microcatheter will be used for selective catheterization of a segmental or subsegmental hepatic artery branch. Up to two 2 ml vials of 100-300 μ m LC-BeadsTM impregnated per manufacturer-supplied protocol with 25mg of doxorubicin per ml of beads will be administered into the catheterized hepatic artery. Procedure will be stopped when arterial flow approaches stasis and/or when the entire DEB dose has been administered.

Patients will be on bed rest for approximately 4-8 hours following removal of the femoral artery catheter. Per institutional standard, they will be admitted for planned overnight observation to the hospital and discharged once determined to be in stable condition. Management after each DEB-TACE procedure will be according to institutional standard of care.

Patient follow-up is summarized in section 8.4 and section 8.4.1.

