4.0 ELIGIBILITY CRITERIA

4.1 Subject Population

Patients with liver-only HCC UNOS stage T1, T2, or T3 being considered for liver transplantation at UCSF will be eligible. Patients who have undergone prior resection, chemoembolization, radioembolization, bland embolization, ablative therapy or systemic therapy will be eligible to participate in the study.

Treatment with DEB-TACE will be offered to patients being considered for liver transplantation under one of the following protocols:

1. Milan criteria: One lesion less than 5 cm or up to 3 lesions each less than 3 cm.
2. UCSF Downstaging criteria: One lesion less than 8 cm or 2-3 lesions each less than 5 cm with sum of maximum dimensions less than 8 cm, or 4-5 lesions each less than 3 cm with sum of maximum dimensions less than 8 cm.
3. UCSF All-Comers criteria: UNOS stage T3 disease beyond UCSF Downstaging Criteria.

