6. INR > 2.5
7. Serum creatinine > 1.5 mg/dl
8. Macrovascular tumor invasion of portal and/or hepatic vein(s)
9. Extracapsular tumor extension
10. Extrahepatic disease
11. Hepatic encephalopathy refractory to medical therapy
12. Active uncontrolled infection
13. Imaging evidence of common bile duct obstruction
14. Previous sphincterotomy or bilio-enteric anastomosis
15. Significant hepatic arterial to portal vein shunting in the area to be treated.
16. Symptomatic congestive heart failure (CHF)
17. Allergy to or intolerance of prior doxorubicin-based TACE
18. Allergy to or intolerance to iodinated contrast media despite standard of care pre-medication
19. Any contraindications to treatment with LC Bead™ device (e.g. patients with large diameter arteriovenous shunts or patients with a right-to-left shunt).
20. Systemic therapy with sorafenib or other systemic chemotherapeutic agent(s) less than 1 week prior to first planned DEB-TACE.
21. Active second malignancy other than non-melanoma skin cancer or cervical carcinoma in situ. (Patients with history of malignancy are not considered to have a “currently active” malignancy if they have completed therapy and are now considered by their physician to be at less than 30% risk for relapse.)
22. Uncontrolled intercurrent illness including, but not limited to: Ongoing or active infection, symptomatic congestive heart failure, unstable angina pectoris, uncontrolled cardiac arrhythmia, uncontrolled peripheral vascular disease, myocardial infarction within preceding 12 months, cerebrovascular accident within preceding 12 months, pulmonary disease impairing functional status or requiring oxygen, impairment in gastrointestinal function that may affect or alter absorption of oral medications (such as malabsorption or history of gastrectomy or bowel resection).
23. Pregnant or lactating women are excluded from this study because of the potential for teratogenic or abortifacient effects. Because there is an unknown but potential risk for adverse events in nursing infants secondary to treatment of the mother with DEB-TACE, breastfeeding must be discontinued for eligibility.
24. Psychiatric illness, other significant medical illness, or social situation which, in the investigator’s opinion, would limit compliance or ability to comply with study requirements.

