8.1 Screening/Baseline

Prior to enrollment, patients will be seen by a hepatologist and/or a medical oncologist at UCSF and evaluated for all possible treatment options, one of which will include DEB-TACE. Prior to enrollment, all patients will be discussed in the multidisciplinary liver tumor board, which

includes hepatologists, medical and surgical oncologists, and interventional radiologists. If the patient is deemed a good candidate for the procedure, the patient will then be referred to the interventional radiologist for DEB-TACE. Patients will be offered the opportunity to be screened for study participation. After informed consent is obtained, pre-procedure assessment is summarized in Table 1.

Approximately zero to sixty days prior to DEB-TACE, the following will be performed to determine eligibility:

- cross sectional imaging of the abdomen using multi-phase CT or MRI with IV contrast
- CT scan of chest (with and/or without contrast)
- baseline laboratory tests
- clinical history and physical examination

Approximately zero to twelve days prior to DEB-TACE, the following additional procedures will be performed (if the initial screening is performed outside 12-day window):

- Laboratory testing including liver function tests, CBC, BUN, creatinine, coagulation profile, and serum alpha-fetoprotein level
- Medical history and physical examination
- ECOG performance status

Baseline cardiac function monitoring using echocardiogram will be performed approximately zero to 720 days prior to first planned DEB-TACE

One day prior to DEB-TACE, the UCSF Inpatient Pharmacy will be instructed by the interventional radiologist to start incubation of two 2ml vials of 100-300 μ LC Beads[®] with 100mg doxorubicin (25mg/ml of beads) per manufacturer-supplied instructions for use (currently not cleared by the FDA for use).

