9.2.2 RECIST Guidelines

- All measurements should be taken and recorded in metric notation, using a ruler or calipers.
- All baseline evaluations should be performed as closely as possible to the beginning of treatment and never more than 4 weeks before the beginning of the treatment.
- Assessment will be performed using conventional imaging methods (CT, MRI).
- The same method of assessment and the same technique should be used to characterize each identified and reported lesion at baseline and during follow-up.
- Up to three measurable lesions will be identified as target lesions. Target lesions will be selected on basis of size (lesions with the longest diameter) and their suitability for accurate repeated measurements (lesions can be located/identified during follow-up as well as baseline).
- Target lesions will be measured in one dimension. A sum of the longest diameter (LD) for all target lesions will be calculated and reported as the baseline sum LD. The baseline sum LD will be used as reference by which to characterize the objective tumor.

All other lesions (or sites of disease) should be identified as non-target lesions and should also be recorded at baseline. Measurements of these lesions are not required, but the presence or absence of each should be noted throughout follow-up.

9.2.3 mRECIST Definitions (See Appendix 4)

Measurable Disease: The presence of at least one measurable lesion.

Measurable Lesion: The lesion can be accurately measured in at least one dimension [longest diameter to be recorded] as ≥ 10 mm with spiral CT or MRI scan.

Nonmeasurable Lesion: All other lesions, including small lesions [<10 mm with spiral CT scan or MRI] and truly nonmeasurable lesions (infiltrative lesions).

Complete Response (CR): Disappearance of any intratumoral arterial enhancement in all target lesions

Partial Response (PR): 30% decrease in the sum of diameters of viable (enhancement in the arterial phase) target lesions, taking as reference the baseline sum of the diameters of target lesions

Stable Disease (SD): Any cases that do not qualify for either partial response or progressive disease

Progressive Disease (PD): An increase of at least 20% in the sum of the diameters of viable (enhancing) target lesions, taking as reference the smallest sum of the diameters of viable (enhancing) target lesions recorded since treatment started

9.2.4 mRECIST Guidelines (See Appendix 4)

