- All eligible patients with measurable disease *at baseline* will be included in the analysis for efficacy.
- All measurements should be taken and recorded in metric notation, using a ruler or calipers.
- All baseline evaluations should be performed as closely as possible to the beginning of treatment and never more than 4 weeks before the beginning of the treatment.
- Assessment will be performed using conventional imaging methods (CT, MRI).
- The same method of assessment and the same technique should be used to characterize each identified and reported lesion at baseline and during follow-up.
- Up to three measurable lesions will be identified as target lesions. Target lesions will be selected on basis of size (lesions with the longest diameter) and their suitability for accurate repeated measurements (lesions can be located/identified during follow-up as well as baseline).
- Target lesions will be measured in one dimension. A sum of the longest diameter (LD) for all target lesions will be calculated and reported as the baseline sum LD. The baseline sum LD will be used as reference by which to characterize the objective tumor.
- All other lesions (or sites of disease) should be identified as non-target lesions and should also be recorded at baseline. Measurements of these lesions are not required, but the presence or absence of each should be noted throughout follow-up.

The measurement of the longest diameter of the viable tumor may be challenging in lesions showing partial internal necrosis. The following points should be taken into account in such cases:

- The measurement of the viable tumor should be performed on CT or MRI obtained in the arterial phase, when the contrast between viable vascularized tumor tissue and nonenhancing necrotic tissue is the highest.
- The longest diameter of the viable tumor is not necessarily located in the same scan plane in which the baseline diameter was measured: a thorough careful evaluation of the CT or MRI scans is required.
- The measurement of the viable tumor diameter should not include any major intervening areas of necrosis.

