10.3 CRITERIA FOR PATIENT REMOVAL FROM STUDY

Patients will be removed from study for any of the following events:

- Unacceptable toxicity (listed above in section 10.1),
- Other toxicity which investigator deems to place the patient at significant risk for toxicity
- Withdrawal of consent
- Noncompliance or inability to meet requirements of protocol
- Requirement for >4 DEB-TACE procedures
- Requirement for another anti-cancer treatment modality such as ablation, surgery, conventional TACE
- Receives a liver transplant
- Develops untreatable intrahepatic tumor progression
- Develops extrahepatic tumor progression

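### The scan used as response baseline is not required to follow the last prior anti-cancer therapy, so another treatment's effect can be counted as DEB-TACE response

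*Combined protocol and SAP*

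**What the plan says.** Section 4.1 admits patients with earlier treatment: "Patients who have undergone prior resection, chemoembolization, radioembolization, bland embolization, ablative therapy or systemic therapy will be eligible to participate in the study". Section 4.3 then sets two wash-outs, both counted back from DEB-TACE:

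- Item 1, local therapy, excludes "Liver-directed therapy (chemoembolization, radioembolization, bland embolization, ablative therapy) within 4 weeks of DEB-TACE".
- Item 20, systemic therapy, excludes "Systemic therapy with sorafenib or other systemic chemotherapeutic agent(s) less than 1 week prior to first planned DEB-TACE".

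The age of the baseline abdominal scan is given in two ways:

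- Section 3.1: "One to sixty days prior to treatment, patients will undergo imaging of the abdomen with contrast-enhanced CT or MRI". Section 8.1 lists abdominal imaging under "Approximately zero to sixty days prior to DEB-TACE, the following will be performed to determine eligibility". The schedules in section 8.0 show one pre-treatment abdominal scan, in the column for days -60 to 0. Section 8.1 repeats laboratory tests, history, examination and performance status when screening falls outside 12 days, but not the scan.
- Sections 9.2.2 and 9.2.4, which govern response measurement, say that baseline evaluations are "never more than 4 weeks before the beginning of the treatment".

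Section 9.2 measures response against that scan: "The baseline sum LD will be used as reference by which to characterize the objective tumor". The result feeds the primary efficacy analysis (section 12.3), the stage 1 stop at 4 or fewer responses in 17, and the final criterion of 14 or fewer in 51 (sections 10.2 and 12.2). No section ties the date of the scan to the end of earlier anti-cancer therapy.

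**The concern.** A wash-out protects a change-from-baseline endpoint only if the baseline is measured after the earlier treatment has ended. Here the wash-outs are counted from DEB-TACE, and the scan may come before the earlier treatment or during it. If that treatment shrinks a target lesion, or removes its arterial enhancement, after the scan and before DEB-TACE, the change seen one month after the last DEB-TACE contains both effects.

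The trial has a single arm, so no control group would show this. A response carried over in this way counts in favour of DEB-TACE. It raises the chance of declaring an inactive treatment worth pursuing and lowers the chance of stopping at stage 1.

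**Working it through.** **1. Reproduce the design.** Inputs from sections 12.1 and 12.2: unacceptable rate 20%, target rate 40%, stages of 17 and 34, stop at 4 or fewer of 17, negative at 14 or fewer of 51.

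- P(stop at stage 1) = P(X₁ ≤ 4), with X₁ ~ Bin(17, p).
- P(positive) = Σ over x = 5 to 17 of P(X₁ = x) · P(X₂ ≥ 15 − x), with X₂ ~ Bin(34, p).

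At p = 0.20 the stage 1 stop is 0.758 and the type I error 0.0487. At p = 0.40 the stage 1 stop is 0.126 and the power 0.854. The plan states 76%, 5%, 13% and 85%, so its figures reproduce.

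**2. Days in which therapy can follow the scan and still respect the wash-out.** Gap = oldest permitted scan − wash-out, not below zero.

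| Oldest scan | Local (28-day wash-out) | Systemic (7-day wash-out) |
|---|---|---|
| 60 days (3.1, 8.1, schedule) | 60 − 28 = 32 (days -60 to -29) | 60 − 7 = 53 (days -60 to -8) |
| 28 days (9.2.2, 9.2.4) | 28 − 28 = 0 | 28 − 7 = 21 (days -28 to -8) |

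The local gap depends on which window governs. The systemic gap exists under both: a scan on day -28 with systemic therapy continuing to day -8 breaks no stated rule.

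**3. Illustrative effect on the decision rules.** Let f be the share of patients whose prior therapy falls in the gap, and q the chance that this therapy alone makes the patient a responder. Assume a true DEB-TACE rate of 20% and independent effects. The observed rate is then

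p = (1 − f)·0.20 + f·[1 − 0.80·(1 − q)] = 0.20 + 0.80·f·q.

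The documents give no f. The 10% for q is an assumption; 35-40% is the objective response rate that section 1.1 gives for TACE.

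| q | f | p | Type I error | Stage 1 stop |
|---|---|---|---|---|
| none | 0 | 0.200 | 4.9% | 75.8% |
| 10% | 1% | 0.2008 | 5.0% | 75.5% |
| 10% | 2% | 0.2016 | 5.2% | 75.3% |
| 10% | 5% | 0.204 | 5.6% | 74.4% |
| 10% | 10% | 0.208 | 6.5% | 73.0% |
| 35-40% | 5% | 0.214-0.216 | 7.9-8.4% | 70.9-70.2% |
| 35-40% | 10% | 0.228-0.232 | 11.9-13.2% | 65.8-64.3% |

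The rows with q of 35-40% use a TACE rate. They bear only on local therapy, and only if the 60-day window governs.

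**The case against.** The strongest reply is that sections 9.2.2 and 9.2.4 already limit the response baseline to 4 weeks. A reader might infer that a patient scanned on day -55, given ablation or conventional TACE on day -35 and treated on day 0 meets every rule. The documents do not support that: the day -55 scan satisfies sections 3.1 and 8.1 but breaches 9.2. If the 4-week limit governs, the local gap is zero, and the larger type I errors go with it. This stands. However, the sections that schedule the scan say 60 days, so staff who follow them leave the gap open.

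Other safeguards narrow the route without closing it.

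- Section 8.1 places tumor board review and referral for DEB-TACE before screening, which makes an intervening local procedure less likely.
- Section 10.3 removes patients for "Requirement for another anti-cancer treatment modality such as ablation, surgery, conventional TACE". This limits new treatment on study, but does not clearly reach therapy before enrollment or systemic therapy already under way at the scan.
- The primary endpoint covers treated lesions only, so the earlier therapy must have acted on a lesion that DEB-TACE later treats.

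It is also fair to say that the net direction is not certain. Tumor growth between an old scan and DEB-TACE, or after systemic therapy stops, works against a response. Only the carry-over component favours DEB-TACE. Finally, for systemic therapy the documents give neither a response rate nor the share of patients affected, and with a 10% response and few patients affected the effect is small.

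**Conclusion.** The gap is real. No section requires the baseline scan to follow the last prior therapy, and for systemic therapy this leaves 53 or 21 unprotected days, depending on the window. For local therapy the figure is 32 or 0 days, so that part is first a contradiction between sections 3.1, 8.1 and the schedule on one side and 9.2.2 and 9.2.4 on the other.

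The size of any bias cannot be computed from the documents. With a true rate of 20% and independent effects, both assumed, type I error is 5.0-5.6% if 1-5% of patients are affected and the prior-therapy response is 10%. It is about 8% at 5% affected and 12-13% at 10% affected with a 35-40% response, on the local route under the 60-day window only.

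A reader might infer that earlier treatment effects will be scored as DEB-TACE response and that the error rate is badly inflated. The documents support only that they can be. Neither a material inflation nor a critical grade is established. The sample size calculation is not affected. Whether stable disease counts as a response (included in section 10.2, while section 12.1 speaks of objective response) is a separate question that would change how much carry-over matters.

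**What to change.** 1. Reconcile the 60-day baseline imaging window (sections 3.1 and 8.1, schedule) with the 4-week limit (sections 9.2.2 and 9.2.4).
2. State in sections 8.1 and 9.2 that the scan used as RECIST and mRECIST baseline must be obtained after the last prior liver-directed or systemic anti-cancer therapy.
3. Record the date of the last prior therapy and the date of the baseline scan for every patient.
4. Add to section 12.3 a sensitivity analysis of the primary response that excludes any patient whose baseline scan precedes the end of prior therapy.

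Reconciling the windows is not enough by itself, because the 21-day systemic gap remains under the 4-week limit. The wash-out periods, treatment, sample size and decision rules stay as they are. The cost is one sentence in each of two sections, two date fields and one extra analysis. A few patients would be scanned later in the window or have the screening scan re-timed.

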6. INR > 2.5
7. Serum creatinine > 1.5 mg/dl
8. Macrovascular tumor invasion of portal and/or hepatic vein(s)
9. Extracapsular tumor extension
10. Extrahepatic disease
11. Hepatic encephalopathy refractory to medical therapy
12. Active uncontrolled infection
13. Imaging evidence of common bile duct obstruction
14. Previous sphincterotomy or bilio-enteric anastomosis
15. Significant hepatic arterial to portal vein shunting in the area to be treated.
16. Symptomatic congestive heart failure (CHF)
17. Allergy to or intolerance of prior doxorubicin-based TACE
18. Allergy to or intolerance to iodinated contrast media despite standard of care pre-medication
19. Any contraindications to treatment with LC Bead™ device (e.g. patients with large diameter arteriovenous shunts or patients with a right-to-left shunt).
20. Systemic therapy with sorafenib or other systemic chemotherapeutic agent(s) less than 1 week prior to first planned DEB-TACE.
21. Active second malignancy other than non-melanoma skin cancer or cervical carcinoma in situ. (Patients with history of malignancy are not considered to have a “currently active” malignancy if they have completed therapy and are now considered by their physician to be at less than 30% risk for relapse.)
22. Uncontrolled intercurrent illness including, but not limited to: Ongoing or active infection, symptomatic congestive heart failure, unstable angina pectoris, uncontrolled cardiac arrhythmia, uncontrolled peripheral vascular disease, myocardial infarction within preceding 12 months, cerebrovascular accident within preceding 12 months, pulmonary disease impairing functional status or requiring oxygen, impairment in gastrointestinal function that may affect or alter absorption of oral medications (such as malabsorption or history of gastrectomy or bowel resection).
23. Pregnant or lactating women are excluded from this study because of the potential for teratogenic or abortifacient effects. Because there is an unknown but potential risk for adverse events in nursing infants secondary to treatment of the mother with DEB-TACE, breastfeeding must be discontinued for eligibility.
24. Psychiatric illness, other significant medical illness, or social situation which, in the investigator’s opinion, would limit compliance or ability to comply with study requirements.

4.4 Subject Selection

Participants who meet the eligibility criteria above will be evaluated by the UCSF liver tumor board, which consists of Hepatology, Medical Oncology, Transplant Surgery, and Interventional Radiology services. The team will determine which patients should be offered this therapy. Patients who meet eligibility criteria will be referred for possible treatment.

